4.1 Inclusion criteria

Each patient must meet all of the following inclusion criteria to be enrolled in the study.

- 1) The subject is scheduled for elective laparoscopic ventral hernia repair;
- 2) The subject is ≥ 18 years and ≤ 80 years;
- 3) The patient agrees to receive a quadratus lumborum block
- 4) American Society of Anesthesiologists class 1-3.

4.2 Exclusion criteria

Patients meeting any of the following exclusion criteria are not to be enrolled in the study.

- 1) Subject is < 18 years of age or >80 years of age;
- 2) Subject is non-English speaking;
- 3) Subject is known or believed to be pregnant;
- 4) Subject is a prisoner;
- 5) Subject has impaired decision-making capacity per discretion of the Investigator;
- 6) Significant renal, cardiac or hepatic disease per discretion of the investigator;
- 7) American Society of Anesthesiologists class 4-5;
- 8) Known hypersensitivity and/or allergies to local anesthetics;
- 9) Chronic opioid use (daily or almost daily use of opioids for > 3 months at any point in their lives).
- 10) Repair of a recurrent ventral hernia
- 11) Repair of multiple ventral hernias
- 12) Unobtainable sonographic views
- 13) Lacking health insurance

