6.2 Recruitment and consent

For those patients meeting criteria, they will be approached by the anesthesiologist designated to care for them on the day of surgery. That anesthesiologist will then recruit the patient for the study in the pre-operative holding area. In order to ensure the candidate's privacy and confidentiality, the discussion will take place in pre-operative holding area with the cubicle's curtain and room door closed. In a tone of voice insufficient for others to overhear the conversation and in the presence of only those immediately accompanying the patient and those who are directly involved with the patient's care, the

candidate's eligibility will again be verified against the study enrollment criteria. For candidates with confirmed study enrollment eligibility, the study purpose, procedures, risks, benefits, and alternatives will then be discussed by a study staff member. The written information about the study provided to the candidate at the time of their check-in will be reviewed and they will be instructed to take up to 90 minutes to consider participation. A study member will conduct the informed consent discussion and obtain informed consent and a study physician will be available at all times for any consent-related questions. Any questions that the candidate may have will be answered. Undue coercion will be prevented by stressing that the potential subject does not have to agree to participation and that the future care of the potential subject will not change regardless of the decision about participation. If the candidate has no further questions and would like to participate, they will be asked to sign the written informed consent document.

7. Activities and measurements

Prior to the procedure:

The subject will be met in the preoperative area by a staff anesthesiologist, who interviews and examines the subject. A full explanation of general anesthesia and quadratus lumborum block, including risks, benefits, and alternatives, will be given and informed consent for anesthetic services obtained.

Subjects will be asked to rate their pain at rest using a Numerical Rating Scale (NRS) (0-10) where 0 represents no pain and 10 represents the worst pain imaginable.

Study Randomization:

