After completion of pre-operative check in and consent is obtained by the staff anesthesiologist, the subject will be randomized to receive or not receive QLB. Randomization will be determined by opening a sequential, pre-sealed envelope with the group assignment designated within. If assigned to the intervention arm, they will then be prepped for QLB.

Quadratus Lumborum Block Procedure:

The block will be performed in the preoperative holding room as is standard practice at UW Health at the American Center. An intravenous catheter will be placed, and the subject will be pre-medicated with midazolam and/or fentanyl as needed at the discretion of the staff anesthesiologist.

Quadratus lumborum blockade will be performed after positioning the patient in the lateral decubitus position with the assistance of ultrasound guidance in the mid-abdomen posterior to the mid-axillary line. A Stimuplex needle (B. Braun Medical Inc., Melsungen, Germany) will be inserted in-plane to the ultrasound probe until the tip of the needle is appropriately positioned. Thirty milliliters of 0.25% bupivacaine will be injected under ultrasound guidance after negative aspiration. The procedure will then be repeated on the opposite side, maintaining sterility and, again, injecting 30 mL of 0.25% bupivacaine. The Bupivacaine mixture will be mixed with 2.5mcg epinephrine/ml of solution as an intravascular marker which is standard in most peripheral nerve blocks. In a situation where a patient is less than 60kg, a weight-based adjustment will be made to adjust dosing to the clinically accepted standard of 0.25mg/kg of bupivacaine. In the rare event that sonographic views are unobtainable, the patient will be excluded from the study. This outcome is unlikely to be clinically significant as qualification for laparoscopic ventral hernia repair has its own cutoff for body mass index and blocks are very rarely abandoned. However, for patient safety, we reserve the right to abandon a block.

During the Surgical Procedure:

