9.1 Potential risks

Standard of care is currently for patients presenting for ventral hernia repair to receive medical management without a regional anesthetic technique although it is reasonable and clinically accepted to offer truncal blocks, such as the QL block, in patients whom it is suspected will be challenging in terms of their pain control or may be particularly sensitive to opiate narcotics. Patients in the control arm face no additional risk. For patients in the intervention arm, risks for quadratus lumborum blockade involve bleeding, infection, and nerve damage at the site of injection. Risks associated with the use of bupivacaine include allergic reaction or inadvertent intravascular injection. Other adverse reactions such as nausea, vomiting, and constipation are possible. All of these adverse effects are extremely rare.

Risks associated with loss of confidentiality

There is a risk that information recorded about subjects will be shared with people who would not normally have access to this information.

Unknown risks

This study may involve risks to the subject which are currently unforeseeable. We will inform subjects as soon as possible if we discover any information that may affect the subject's health, welfare, or decision to be in this study.

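### Block suitability is not confirmed before the envelope is opened: Section 4.2 does not cover the block harms named in Section 9.1, and what is missed surfaces only in the QLB arm

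*Combined protocol and SAP*

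**What the plan says.** **Risks.** Section 9.1 states that "risks for quadratus lumborum blockade involve bleeding, infection, and nerve damage at the site of injection". It lists the drug risks separately: "Risks associated with the use of bupivacaine include allergic reaction or inadvertent intravascular injection".

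**Selection.** Three of the 13 exclusions in Section 4.2 bear on these risks or on whether the block can be done: "Known hypersensitivity and/or allergies to local anesthetics" (criterion 8), "Unobtainable sonographic views" (criterion 12) and, more loosely, "Significant renal, cardiac or hepatic disease per discretion of the investigator" (criterion 6). Criterion 7 excludes ASA class 4-5. Inclusion criterion 3 in Section 4.1 asks for the patient's agreement to a block, which is not a clinician's judgement that the patient is suitable for one.

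**Mitigation.** Section 9.2 relies on dose control, ultrasound guidance, sterile technique and specialist supervision. It does not mention patient selection.

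**Order of events.** Under Section 7, Prior to the procedure: "The subject will be met in the preoperative area by a staff anesthesiologist, who interviews and examines the subject". The envelope is opened next. Then: "If assigned to the intervention arm, they will then be prepped for QLB". Under the block procedure in Section 7, patients whose views cannot be obtained are excluded from the study, and "for patient safety, we reserve the right to abandon a block".

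**Withdrawal and analysis.** Section 7.2 lets the care team or a study physician withdraw a subject before or during the intervention period. Section 8 specifies intent-to-treat analysis by assigned arm. Section 11.1 leaves out of the final study the data of a subject who withdraws prematurely.

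**The concern.** The plan uses exclusion criteria to settle some aspects of block suitability, but not for the three harms that it lists first. A patient at raised risk of one of them is eligible as written if the other criteria are met. Examination before randomisation gives an opportunity to notice this. Nothing says that the envelope stays closed until block suitability has been judged, and nothing is recorded.

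If the matter is noticed only when the block is being prepared, two things are at stake.

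- **Safety.** The patient either receives the two injections or has the block withheld after allocation. An earlier check would avoid that choice.
- **Comparability.** Only QLB-assigned patients reach this step, so control patients with the same features are not sorted out in the same way. If the patient is analysed as assigned, the expected difference in POD1 pain is diluted. If the patient is excluded or withdrawn and the data dropped, one arm loses selected patients and the other does not.

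**Working it through.** **1. Risks against selection**

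| Risk in Section 9.1 | Criterion in Section 4.2 that addresses it |
|---|---|
| Bleeding | None |
| Infection | None |
| Nerve damage | None |
| Allergic reaction | Criterion 8 |
| Intravascular injection | None (handled by technique in Sections 7 and 9.2) |

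Criteria 6 and 7 overlap in part. They concern organ disease at the investigator's discretion and overall ASA class, and neither refers to the block harms.

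**2. The plan's sample size**

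Inputs from Section 8.1: difference 2 NRS, SD 2.2, type 1 error 0.05, power 80%. The section does not state sidedness; two-sided is assumed.

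Standardised effect = 2 / 2.2 = 0.909. A two-sample t-test needs 20.002 per group, which rounds up to the stated 21. Power is 82.0% at 21 per group and 86.9% at 24. The increase from 21 to 24 allows for a loss of 1 - 21/24 = 12.5%.

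**3. Dilution if patients stay in the assigned arm**

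Let w be the fraction of QLB-assigned patients who get no block, and assume they gain no benefit.

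- Expected difference: d = 2 × (1 - w)
- QLB-arm variance: 2.2² + 4 × w × (1 - w) (a mixture of blocked and unblocked patients)
- Pooled SD: square root of the average of that variance and 2.2²
- Power: noncentral t, two-sided 0.05

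Example for w = 1/24: d = 2 × 23/24 = 1.917. QLB-arm variance = 4.84 + 4 × (1/24) × (23/24) = 5.000. Pooled SD = √((4.84 + 5.000)/2) = 2.218. Effect = 1.917/2.218 = 0.864.

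| Withheld | d | Power, 21 per group | Power, 24 per group |
|---|---|---|---|
| 0 | 2.00 | 82% | 87% |
| 1% | 1.98 | 81% | 86% |
| 2% | 1.96 | 80% | 85% |
| 1 in 24 (4.2%) | 1.92 | 78% | 83% |
| 2 in 24 (8.3%) | 1.83 | 74% | 79% |
| 3 in 24 (12.5%) | 1.75 | 69% | 75% |

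Every rate in the first column is an assumption. Without the added mixture variance, power is at most about 2 percentage points higher (for example 77% rather than 75% in the last cell).

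**4. If such patients are instead removed from the QLB arm**

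With 3 removed (21 against 24) and an undiluted difference of 2 NRS, power is 84.5%, against 86.9% with none removed. The cost here is not power: the two arms are no longer the groups that were randomised.

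**5. Which route the plan takes**

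Section 8 implies step 3. The exclusion for unobtainable views in Section 7 implies step 4. Section 11.1 would also imply step 4 if a patient whose block is withheld counts as withdrawn, which no passage settles.

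**The case against.** The strongest reply is that the plan already gives clinicians room to act before allocation. Every subject is interviewed and examined by a staff anesthesiologist, eligibility is verified again on the day (Section 6.2), the block's risks are discussed, and Section 7.2 allows withdrawal before the intervention in either arm. This stands. A reader might infer that the right to abandon a block is the first chance to act on patient safety, or that control patients at raised risk can never be identified. The documents support neither reading. What is missing is a stated requirement and a record, not an opportunity.

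Three further points stand in whole or in part.

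- **Depth of injection.** A reader might describe the exposure as two deep injections. Section 1.1 says that the QL2 approach used here has the more superficial needle path. The injections are bilateral, but the documents do not call them deep.
- **Frequency.** Section 7 calls abandoned blocks very rare for any reason, and Section 9.1 calls the adverse effects extremely rare. It would be tempting to report a drop to 69% or 75% as the expected loss. That needs 3 of 24 blocks withheld, and no passage supports such a rate. At 1% to 2%, the 80% target is still met.
- **Unnamed conditions.** No passage says in which conditions this site would withhold a block, so the existence of such patients in this elective ASA 1-3 population is inferred.

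These points limit the size of the problem. They do not supply the missing check, and they do not reconcile Sections 7 and 11.1 with Section 8.

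**Conclusion.** The gap between Sections 4.2 and 9.1 is real on the text, and no passage makes block suitability a condition of opening the envelope. Patients missed by the discretionary safeguards come to light after allocation and in the QLB arm only. How they would then be analysed is unclear, because Section 8 keeps them while Sections 7 and 11.1 may remove them.

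Severity is minor. The power figures assume a two-sided test, no benefit without the block, and withholding rates that the documents do not give. On the evidence available the loss is probably small: power remains at or just above 80% with 21 per group if 1% to 2% of blocks are withheld. The case for change rests more on safety and on keeping the randomised groups intact than on power.

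**What to change.** 1. **Section 4.2.** Reconcile the exclusions with the risks in Section 9.1 by adding a block-suitability criterion. Its content is for the trial's clinicians to define.
2. **Section 7, Prior to the procedure.** Have the staff anesthesiologist confirm and record block suitability for every subject at the existing examination, before the envelope is opened.
3. **Sections 7, 8 and 11.1.** State that once the envelope is opened, a patient whose block is withheld or abandoned stays in the assigned arm for analysis. Reconcile the exclusion for unobtainable views in Section 7 and the dropping of withdrawn subjects' data in Section 11.1 with that rule.

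The exclusion line alone would not resolve the conflict over withdrawn subjects, so item 3 is needed as well. The cost is one criterion, one box on the case report form and a few sentences of text. The planned 21 and 24 per group do not change. The downside is that a few otherwise eligible patients will not be enrolled.

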2.2 Secondary outcomes and endpoints

The secondary outcomes of this study are to compare the following perioperative variables:

Preoperative Variables:

- Baseline pain

Intraoperative Variables:

- Opioid consumption
- Additional analgesics
- Anti-emetic administration

PACU Variables:

- Pain at rest
- Pain with activity
- Nausea
- Numbness distribution
- Opioid consumption
- Time in PACU (duration)
- Time to discharge home (duration)
- Location of most severe pain

POD 1, 2, and 7 Variables:

- Pain at rest

- Pain with activity
- Opioid consumption in morphine equivalents
- Nausea necessitating treatment
- Location of most severe pain
- Satisfaction with perioperative care

3. Study design

This study is a prospective, single-center, randomized trial in which 48 subjects will be enrolled at the University of Wisconsin Hospitals and Clinics (UWHC). The details of the power analysis can be found below. These subjects must meet study eligibility criteria and be scheduled to undergo an elective laparoscopic ventral hernia repair. These subjects must also agree to undergo quadratus lumborum block for postoperative analgesia. Patients will be randomized to receive QLB in addition to medical management or medical management alone. Recovery characteristics, including pain scores, nausea, opioid consumption, duration of time in PACU and to discharge, will be evaluated.

4. Study population

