8.1 Sample size determination

The primary outcome for this study will compare resting NRS pain scores on POD1 between the QLB and medical management groups. A previous study of laparoscopic ventral hernia surgery reported an average POD1 pain score of 4.5 +/- 2.2 NRS (Fields et al, 2015). This average pain score is in keeping with our experience with patients after having laparoscopic ventral hernia surgery at UW-Madison. We feel that a reduction in pain of 2 NRS on POD1 would be meaningful for patients and their physician teams. Therefore, we will power this study to an effect size of 2 NRS. We will accept a type 1 error rate of 0.05 and 80% power. Using these metrics, the study will require a sample size of 21 patients in each group to

detect a statistical difference. To account for patients dropping out or not completing the study, we will enroll 24 patients in each group for a total of 48 patients.

9. Risks and benefits of trial participation

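### The only opioid exclusion tests lifetime duration, not current use, so patients in daily use for 3 months or less up to surgery are eligible and their habitual dose can enter the secondary opioid endpoint

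*Combined protocol and SAP*

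**What the plan says.** Criterion 9 in section 4.2 excludes "Chronic opioid use (daily or almost daily use of opioids for > 3 months at any point in their lives". The inclusion criteria in section 4.1 do not mention opioids, and no other exclusion does.

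Section 2.2 lists "Opioid consumption in morphine equivalents" among the POD 1, 2 and 7 variables. It lists baseline pain as a preoperative variable but not baseline opioid use, and it describes no subtraction of a preoperative dose.

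The primary endpoint is pain: "The primary outcome for this study will compare resting NRS pain scores on POD1 between the QLB and medical management groups" (section 8.1).

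Footnote 3 to the Schedule of Activities requires regular home medications, and those taken before arrival on the day of surgery, to be recorded. Section 5 describes 1:1 allocation and mentions no stratification. Section 8 describes a two-group superiority comparison and names no covariate.

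**The concern.** The criterion turns on how long daily use has ever lasted. Current users who have at some time exceeded 3 months are excluded. Current users who have never exceeded 3 months are not, for example a patient who has taken an opioid daily for the last 10 weeks while waiting for repair.

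For a postoperative consumption endpoint, use at the time of surgery matters directly. A home dose that continues is counted as postoperative consumption whether or not the block works. Such patients may also report pain differently. The plan holds the information needed to identify most of them, but uses it neither for eligibility nor in the analysis.

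At stake is precision. Reducing the need for pain medication is one of the trial's stated aims, and 24 patients per group leave little room for avoidable variance in that endpoint.

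**Working it through.** **Inputs from section 8.1.** The cited study "reported an average POD1 pain score of 4.5 +/- 2.2 NRS". The target difference is 2 points: "Therefore, we will power this study to an effect size of 2 NRS". Type 1 error is set at 0.05 and power at 80%. The stated result is 21 evaluable patients per group, raised to allow for loss: "we will enroll 24 patients in each group for a total of 48 patients". Sidedness is not stated; two-sided is assumed.

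**Step 1: the plan's own figure.** The standardised difference is 2/2.2 = 0.909. The two-sample t-test solution at two-sided 0.05 and 80% power is 20.002 per group, which rounds up to 21. The stated size reproduces. Power is 82.0% at 21 per group and 86.9% at 24. The allowance for loss is 1 − 21/24 = 12.5%.

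**Step 2: effect on the primary endpoint.** Let a share p of enrolled patients be current users whose mean POD1 pain is shifted by d points. The SD becomes √(2.2² + p(1 − p)d²). The documents give neither p nor d; both are assumptions.

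With 4 current users among 48, p = 0.0833 and p(1 − p) = 0.0764:

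| d (NRS points) | SD | Power, 21 per group | Power, 24 per group |
|---|---|---|---|
| none | 2.20 | 82.0% | 86.9% |
| 1 | √(4.84 + 0.076) = 2.22 | 81.4% | 86.4% |
| 2 | √(4.84 + 0.306) = 2.27 | 79.6% | 84.9% |
| 3 | √(4.84 + 0.688) = 2.35 | 76.7% | 82.3% |

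Over a wider range:

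| p | d | SD | n per group for 80% | Power at 21 | Power at 24 |
|---|---|---|---|---|---|
| 5% | 1 | 2.21 | 21 | 81.6% | 86.6% |
| 10% | 2 | 2.28 | 22 | 79.2% | 84.5% |
| 20% | 3 | 2.51 | 26 | 71.3% | 77.2% |

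Power at 24 per group falls below 80% only in the last row, where one patient in five is a current user and the shift is larger than the effect the trial is designed to detect.

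**Step 3: effect on opioid consumption.** The documents give no SD for consumption, so let d be in units of the SD among non-users. The variance is multiplied by 1 + p(1 − p)d²:

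| p | d = 1 SD | d = 2 SD | d = 3 SD |
|---|---|---|---|
| 5% | 1.05 | 1.19 | 1.43 |
| 10% | 1.09 | 1.36 | 1.81 |
| 20% | 1.16 | 1.64 | 2.44 |

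A shift of several SDs is more plausible here than for pain, because the home dose adds directly to the total.

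**Step 4: chance imbalance.** Suppose 4 current users are divided at random between groups of 24:

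- P(4:0 either way) = 2·C(24,4)/C(48,4) = 10.9%.
- P(3:1 either way) = 2·C(24,3)·24/C(48,4) = 49.9%.

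If each continued an assumed 30 mg morphine equivalents a day, a 3:1 split would move the difference in mean daily consumption by (3 − 1)·30/24 = 2.5 mg, and a 4:0 split by 4·30/24 = 5.0 mg. Either direction is equally likely, so the expected shift is zero. Without an SD for consumption, the documents do not allow a judgement on whether 2.5 or 5.0 mg is large.

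**The case against.** The strongest reply is that the gap may be empty. The population is elective, ASA class 1 to 3, with recurrent and multiple hernias excluded, and nothing in the documents suggests that daily opioid use before surgery is common. This stands: the number affected is unknown and could be zero.

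Two further replies also stand. Uneven splits are ordinary chance variation under randomisation; the added variance enters the standard error and does not inflate the type I error. And the cited SD of 2.2 may already include some short-term users, in which case Step 2 counts part of the effect twice.

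A reader might infer that the lifetime wording is itself a fault, because it excludes someone whose only long course ended decades ago. The documents do not support that. Excluding former users adds no noise among those enrolled. The clause is explicit and conservative, and it fits the concern about tolerance and abuse in section 1.1. Its cost is some eligible patients and some generalisability, and nothing shows that recruitment is limited by it.

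A reader might also infer that the primary comparison is biased or the sample size wrong. Neither follows: the expected shift is zero, and the stated 21 per group reproduces.

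Finally, one could leave eligibility alone and adjust for recorded preoperative use. That is a workable fallback, but the plan does not specify it.

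**Conclusion.** The point holds as a gap in the eligibility rule with a modest statistical cost. As worded, criterion 9 admits current daily users who have never exceeded 3 months, and no other section excludes them, stratifies or adjusts for them, or removes their habitual dose from the consumption endpoint.

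The consequence is added between-patient variance, mainly in the secondary opioid endpoints: a factor of 1.05 to 2.44 over the assumed range, and 1.36 in the middle case. For POD1 pain the effect is probably small. These sizes rest on assumed shares and shifts. The gap itself rests only on the text.

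It is worth closing because closing it is cheap and fits the evident aim of keeping opioid-tolerant patients out of the trial.

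**What to change.** Keep the existing more-than-3-months clause, including its lifetime wording. Add to section 4.2 an exclusion for daily or almost daily opioid use within a stated window before the date of surgery, whatever the total duration of that use. The sponsor should set the window. Check it at screening with the home-medication record that footnote 3 already requires.

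The cost is one added line in an amendment and the loss of a few short-term users. Footnote 3 covers regular home medications and those taken before arrival, so it may miss someone who stopped shortly before surgery; one screening question on recent use may be needed.

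If the sponsor prefers to keep current users eligible, section 8 should name recorded preoperative opioid use as a covariate for the consumption endpoints before any data are analysed.
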